6.2.6 SF-36

Health-related quality of life will be assessed using the subject-completed Medical Outcomes Study Short-Form 36 (SF-36), which is a generic health survey that contains 36 questions covering eight domains of health. The SF-36 yields an 8-scale profile of functional health and well-being scores as well as physical and mental component health summary scores. The version 2, 4-week recall questionnaire will be used. Recoding, calculations and standardization will be done as recommended in the User's manual for the SF-36 (Mariush, 2011). Each of the 8 domain scores is the sum of some of the overall 36 item scores.

The initial domain scores are the sum of individual item scores:

- General Health
- Physical Functioning
- Role Physical
- Role Emotional
- Social Functioning
- Bodily Pain
- Vitality

- Mental Health

Domain scores will only be calculated if less than half of the item scores are missing. An imputation method for missing components may be applied as described in Section **5.5.1**.

6.2.7 EQ-5D-5L

A standardized instrument for measuring general health status within the following 5 dimensions:

- Mobility
- Self-care
- Usual activities
- Pain/discomfort
- Anxiety/depression

Each dimension is scored on 5-point scale as:

- 1 = No problems
- 2 = Slight problems
- 3 = Moderate problems
- 4 = Severe problems
- 5 = Extreme problems

General health status is scored on a VAS (0 = poor to 100 = the best). An imputation method for missing components may be applied as described in Section **5.5.1**.

Reduction in the proportion of subjects with problems (moderate, severe or extreme) will represent improvement.

An EQ-5D summary index score can be derived by applying a formula that attaches weights, or index values, to each of the levels in each dimension. The index is calculated by deducting the appropriate weights from the value for full health (i.e., 1). Value sets are country specific and can be obtained from the EuroQol website (EuroQol Research Foundation, 2023).

6.3 Subgroup Analyses

Response rates for the key exploratory efficacy endpoints, as specified in **Table 2**, will be examined using the following subgroups:

- Number of prior biologic and targeted synthetic DMARDs (e.g., < 4 vs. \geq 4)
- Prior use of JAKi (Yes vs. No)
- RA activity at baseline (DAS28-CRP \leq 5.1 vs. DAS28-CRP $>$ 5.1)

- RA severity at initiation of stimulation (< 4 TJC28 or < 4 SJC28 vs. ≥ 4 TJC28 and ≥ 4 SJC28)
- Augmented therapy (yes, no)

After completion of Week 12 assessments, additional treatment for RA may be provided at any time. The decision about the need, type and timing of treatment is left to the discretion of the Co-PI Rheumatologist and the subject. The initiation of these treatments with study treatment during open-label follow-up is considered “augmented therapy”. Subjects combining stimulation with the following additions to RA therapy will fall into the augmented therapy subgroup for analysis of response rates for key exploratory efficacy endpoints at specific timepoints:

- *Prednisone equivalent >10 mg/day.* If average daily corticosteroid use exceeds 10 mg/day prednisone after a period (time from previous visit up to the day before the current visit), the subject is assigned to the augmented therapy subgroup for that visit.
- *Corticosteroid injection.* If subject received a corticosteroid injection within 30 days prior to a study visit, the subject is assigned to the augmented therapy subgroup for that visit.
- *b/ts/csDMARD.* Subjects who receive treatment with biologic, targeted synthetic, or additional conventional synthetic DMARD, or increased dose of background conventional synthetic DMARD will be assigned to the augmented therapy subgroup for all subsequent visits.

7 SAFETY EVALUATION

7.1 AE and SAEs

The incidence of AEs and SAEs in the safety population (see Section 5.2) will be tabulated through Week 264 (end of study). Each AE will be evaluated by clinical investigators in terms of seriousness, severity (i.e., mild, moderate, severe) and strength of relationship (i.e., not related, unlikely related, probably related, definitely related, indeterminate) to the implant procedure, explant procedure, implant device, stimulation and Energizer. Any AE that is determined by a participating investigator to be related (definitely related or probably related) to the implant procedure, explant procedure, implant device, stimulation or Energizer will be categorized as device related.

For all AE tables, a subject reporting the same adverse event more than once will be counted once when calculating the number and percentage of subjects with that particular event. If a subject reports the same AE more than once or has the same AE on multiple occasions, the maximum severity grade and relationship to the study implant and/or study drug will be presented.

The frequencies and percentages of treatment-emergent adverse events will be presented by MedDRA system organ class (SOC) and preferred term (PT). Complete subject listings of all AE will be provided. For each AE the following will be specified: start and stop dates, severity grade, MedDRA SOC and PT, relationship (unlikely related, probably related, definitely related or indeterminate) to the implant procedure, explant procedure, implant device, stimulation or Energizer , and, as well as action taken, outcome of the adverse event, and seriousness.

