4 PROTOCOL SUMMARY

Study Title	Vagus Nerve Stimulation Using the SetPoint System for Moderate to Severe Rheumatoid Arthritis: The RESET-RA Study
Objective	To assess the safety and efficacy of the SetPoint System for the treatment of adult patients with active, moderate to severe rheumatoid arthritis (RA) who have had an inadequate response or intolerance to biologic or targeted synthetic Disease-Modifying Anti-Rheumatic Drugs (DMARDs)
Investigational Device	The SetPoint System
Phase	Phase 3 Pivotal
Study Design	
An operationally seamless, 2-stage, randomized, sham-controlled, double-blind, multicenter pivotal study enrolling at least 240 and up to 250 subjects at up to 45 study centers across the U.S.:
 
 Stage 1 with approximately 60 randomized subjects at up to 25 study centers Stage 2 with approximately 190 randomized subjects at up to 45 study centers, including centers from Stage 1 
There will be a pause in enrollment after enrollment in Stage 1 is completed. This pause in enrollment is intended to allow completion of Week 12 assessments by 60 enrolled and randomized subjects and review of interim analysis results by the independent Data Monitoring Committee (DMC) and the U.S. Food Drug Administration (FDA). The DMC and FDA will confirm whether the study can advance to enroll subjects in Stage 2.
 
After completing primary endpoint assessments at Week 12, there will be a one-way crossover of control subjects to active stimulation and a 252-week open-label follow-up with all subjects (treatment and control) receiving active stimulation to evaluate long-term safety. Blinding will be maintained until the last enrolled and randomized subject in Stage 2 completes Week 12 assessments, and the study dataset for primary analysis is locked.
 
The initial, 12-week follow-up period will generate safety and efficacy data to support an application for Premarket Approval (PMA). The PMA application will also include supporting data on long-term safety for all subjects for whom long-term data are available at the time of application.

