11.10 Explant Procedure

If a subject wants or needs to have their implant removed at the end of the study or earlier, this must be communicated to the study sponsor prior to scheduling or performing the explant procedure. Before the explant procedure, MicroRegulator stimulation must be suspended (see Section 11.8). The surgical investigator will perform pre-surgical clearance testing per standard of care. The surgical investigator will remove the implant according to the explant procedure protocol outlined in SetPoint System Instructions for Use Surgeon Manual. In the event an implant cannot be explanted, it will be decommissioned. In the unlikely event that a failed implant cannot be explanted, and the nature of device failure precludes decommissioning, the subjects will be followed for safety for a period of 10 months, at which point the internal battery would be fully depleted. (see Section 11.9).

The explanted MicroRegulator and POD shall be returned to SetPoint Medical according to the return shipping instructions provided or disposed according to investigator's institutional procedures for disposal of blood contaminated medical devices. Following the explant procedure, subjects will be evaluated to assess for proper wound healing and post-op recovery per standard of care. Once the subject is cleared post-surgery, the subject will exit the study. Any AE resulting from the explant procedure should be followed to resolution.

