11.11 Duration of Study Period

The study duration is approximately 84 months (8 months for enrollment into Stage 1, 6 months for a pause in enrollment after Stage 1, 12 months for enrollment into Stage 2, and approximately 58 months for completion of follow-up).

For a given subject, the maximum study duration is 1,899 days (about 5 years, 3 months):

- 30 days from informed consent to Implant Procedure
- 21 days between Implant Procedure and randomization at Day 0
- 84 days (about 3 months) between initiation of stimulation at Day 0 to Week 12

- 1,764 days (about 4 years, 10.5 months) between Week 12 and Week 264

A timeline of the key study visits is provided in **Figure 13**.

[figure not shown]

Figure 13: SPM-020 Study Timeline

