16.3 Potential Risks with Surgical Implantation

Surgical placement of the implant device can cause damage to the vagus nerve. While the damage typically heals with time, in rare cases it can be permanent. The most significant symptoms from damage to the vagus nerve are hoarseness or other voice changes, breathing or swallowing changes. Swallowing difficulties could lead to aspiration. These risks could occur because nerves that control some throat muscles and the vocal cords come from the vagus nerve.

In rare cases, during the surgery for device placement, other muscles, nerves, blood vessels or tissues in the area can be damaged. Damage to sympathetic innervation to the orbit can result in Horner's Syndrome which includes symptoms of ptosis, meiosis, and anhidrosis. Damage to the vocal cord can result in vocal cord paralysis. Symptoms of vocal cord paralysis include voice changes and difficult breathing, which generally resolve with surgical intervention and voice therapy.

Other risks associated with surgical implantation of MicroRegulator include:

- Complications related to general anesthesia with endotracheal intubation;

- Postoperative pain, redness, itching, swelling or seroma at the implant site;
- Eructation, constipation, vomiting or gagging
- Excessive bleeding due to unanticipated vessel injury; and
- Scarring or infection of the tissues around where the device is placed. Infections usually treated with antibiotics, in rare cases requiring explantation.

The risks associated with the explant procedure in the event the device requires removal needs to be factored into the overall risk assessment when evaluating participation in the clinical study. The safety and impact on vagus nerve function post-device explant is unknown. Preclinical studies in canines show no evidence of implantation site and device fibrosis and vagus nerve viability appears unaffected as assessed by morphologic and histopathologic examination including stains for myelin integrity.

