3.1 Study Objective

The overall objective of this study is to evaluate the safety and efficacy of the SetPoint System for the treatment of adult patients with active, moderate-to-severe RA who have had an inadequate response or intolerance to biologic or targeted synthetic DMARDs.

The specific objective of the open-label follow-up with all subjects receiving active stimulation is to gather long-term safety and exploratory efficacy data.

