6 EXPLORATORY EFFICACY ANALYSES

6.1 General Considerations

For each follow-up time point, all dichotomous variables will be reported as responders / patients who have achieved that follow-up duration, percentage of responders, and 95% CI.

Values will be reported at each follow-up timepoint.

For continuous measures, mean, SD, median, minimum and maximum will be presented at each time point.

Time will be measured from initiation of stimulation. Therefore study participants originally randomized to stimulation will, for example, have Week 24 visits represented at 24 weeks of follow-up while study participants randomized to sham will have Week 24 visits represented as 12 weeks, since they will have been on stimulation on for 12 weeks at the Week 24 visit.

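### Long-term adverse events are planned only as counts and crude percentages, with no patient-years and no stated counting start at first active stimulation

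*SAP*

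**What the plan says.** Long-term safety is a main purpose of the open-label phase. CLP-008 Section 3.1 gives the aim as to "gather long-term safety and exploratory efficacy data", and the Protocol Summary says the marketing application will carry "supporting data on long-term safety for all subjects for whom long-term data are available at the time of application".

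The planned analysis is descriptive. CLP-008 Section 7.1 says "The incidence of AEs and SAEs in the safety population (see Section 5.2) will be tabulated through Week 264 (end of study", and then "The frequencies and percentages of treatment-emergent adverse events will be presented by MedDRA system organ class (SOC) and preferred term (PT"). A subject counts once per event. Treatment-emergent is not defined there. Section 7.3 handles device deficiencies in the same way.

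Tables 14.8.3.1 to 14.8.3.8 have three columns (TOL, COL and Safety). Each gives events and n (%), with that population's size as denominator. Safety is everyone enrolled, that is, everyone in whom implantation was attempted. TOL and COL (CLP-008 Section 5.2) keep only subjects who stayed on active stimulation in the open-label period and have follow-up data.

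Only the efficacy section fixes a time origin: "Time will be measured from initiation of stimulation" (CLP-008 Section 6.1). Section 7 has no counterpart.

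**The concern.** A percentage with a fixed denominator is interpretable when everyone has been observed for about the same time. Here that need not hold. An application-time cut takes whatever follow-up exists, so a subject seen for three months weighs the same as one seen for more than two years. At the end of the study, subjects who left early stay in the Safety denominator as if event-free. Late-onset events are the most exposed to this, because few subjects have yet been at risk for them.

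The TOL and COL columns do not solve the problem. A subject who suspends stimulation or has the implant decommissioned or removed, possibly because of an AE, can fall out of both. It is also unclear whether the COL column starts at crossover or includes the surgical and sham periods. After crossover there is no randomized comparison, so how often events occur per unit of time on active stimulation is the main thing the long-term data can show. The tables leave that out.

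**Working it through.** **The plan's own figures.** Protocol Section 11.11 gives 30 + 21 + 84 + 1,764 = 1,899 days per subject and 8 + 6 + 12 + 58 = 84 months for the study. Both sums reproduce. The plan states no AE rate and no dropout rate, so those below are assumptions shown as ranges.

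**Inputs.** Enrolment is "8 months for enrollment into Stage 1, 6 months for a pause in enrollment after Stage 1, 12 months for enrollment into Stage 2" (Protocol Section 11.11), with 60 and about 190 subjects allocated 1:1. Control subjects start active stimulation at Week 12 (84 days = 2.76 months). The horizon T is 264 weeks, or 1,848 days = 60.7 months. Assumptions: uniform entry within each stage, entry taken as Day 0, a cut when the last subject reaches Week 12, and no earlier losses.

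**Step 1: spread of follow-up at the cut.** The cut falls at 26 + 2.76 = 28.76 months.
- Stage 1 mean: 28.8 - 4 = 24.8 months. Stage 2 mean: 28.8 - 20 = 8.8 months.
- Range since Day 0: 2.8 to 28.8 months.
- Overall mean: (60 × 24.76 + 190 × 8.76)/250 = 12.6 months. This is the mean active exposure for treatment. For control it is 12.6 - 2.76 = 9.8 months.
- About 33% of subjects have 12 months on active stimulation, and 10% have 24 months.

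**Step 2: what a crude percentage shows.** Take a constant hazard λ = -ln(1 - R)/T for a true 264-week risk R. The crude percentage is the average of 1 - exp(-λa) over each subject's active exposure a.

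| | R = 5% | R = 10% | R = 20% |
|---|---|---|---|
| Crude, cut at last subject's Week 12 | 0.9% | 1.9% | 4.0% |
| Crude, cut 6 months later | 1.4% | 2.9% | 6.1% |
| Crude, cut 12 months later | 1.9% | 3.9% | 8.1% |
| Rate per 100 patient-years, any cut | 1.0 | 2.1 | 4.4 |

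The crude figure roughly doubles over a year although the underlying risk has not changed. The rate stays put. For an event that can occur only after 12 months of stimulation, about two thirds of the denominator (100% - 33%) could not yet have had it at the first cut.

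**Step 3: Week 264 with dropout.** Let μ = -ln(1 - d)/T for a dropout proportion d. The crude risk is λ/(λ + μ) × (1 - exp(-(λ + μ)T)). For R = 10% and d = 20% it is 8.98%, a relative shortfall of about 10%. Over R from 5% to 20% the shortfall is:
- 0% with no dropout;
- 5% at d = 10%;
- 10% at d = 20%;
- 20 to 21% at d = 7/18;
- 27 to 28% at d = 50%.

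If the event occurs only in weeks 160 to 264, the shortfall at d = 10%, 20% and 7/18 is 8%, 16% and 32 to 33%. The 7 of 18 is the number who discontinued in the earlier long-term study SPM-006 (Protocol Section 7.3.1), which is only a loose guide.

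**Step 4: the opposite direction.** If a proportion q have the event before active stimulation and counting starts at consent, the tabulated risk is 1 - (1 - q)(1 - R). With R = 10%, q = 5% gives 14.5% and q = 20% gives 28%.

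**Step 5: which window applies to COL.** The introductions to both SAPs confine CLP-008 to open-label data. Protocol Section 17.6 counts AEs from consent to Week 264, and CLP-008 Table 14.8.3.3 tabulates implant-procedure events in every column. CLP-004 Table 14.1.3.2 separates pre-implant events from those at and after implantation. CLP-008 Table 14.8.3.2 does not. The passages leave the window open.

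**The case against.** The sentence in Section 7.1 describes the end-of-study table, and planned follow-up at Week 264 is the same for every subject. That stands: without dropout the crude and true risks agree there, so bias at that point depends on dropout, which the plan does not state. The unequal follow-up comes from an application-time cut that Section 7.1 does not define, and the protocol calls those data supporting. That also stands, but the protocol does foresee such use.

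Four stronger readings are tempting, and the documents do not support them.
- **A reader might infer that the crude figure hides most of the five-year risk.** At an assumed 2 per 100 patient-years, the crude figure measured from Day 0 is 2.1%, against a 264-week risk of 9.6%. But the risk at the mean follow-up is 1 - exp(-0.02 × 12.6/12) = 2.1% as well. The gap measures how young the data are, and no summary of such a cut could close it without extrapolating.
- **A reader might infer that long-term risk is understated throughout.** Step 4 shows that counting from consent raises the percentages.
- **A reader might infer that events on active stimulation cannot be separated from the rest.** CLP-008 has separate tables by relatedness (procedure, device, stimulation, Energizer, explant), and its listings give AE onset dates and each subject's Day 0 and Week 12 dates. A rate can be derived. It is just not planned, and CLP-008 Section 5.1 would class it as post hoc if it were designed after lock.
- **A reader might infer a gap in safety follow-up after explant.** Protocol Section 11.10 says "Once the subject is cleared post-surgery, the subject will exit the study" and Section 16.3 says "The safety and impact on vagus nerve function post-device explant is unknown". But Section 11.10 also has AEs from the explant procedure followed to resolution, and Section 10.4 does the same for ongoing AEs in withdrawn subjects. Visits after exit would be a different design and would need an amendment.

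**Conclusion.** The point holds as an analysis gap. CLP-008 plans long-term AEs and device deficiencies only as counts and crude percentages for TOL, COL and all enrolled subjects. It has no exposure-adjusted summary and no stated counting window from first active stimulation. TOL and COL can also lose subjects who stopped stimulation.

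The effect is conditional. At an application-time cut the percentages would mix exposures that differ about ten-fold, given the planned calendar, uniform entry and a cut at the last subject's Week 12. At Week 264 the relative shortfall for a constant-hazard event is 0% without dropout and about 5 to 28% for 10 to 50% dropout, and larger for late-onset events. Late-onset risk may therefore be understated. If counting starts at consent, surgical and sham-period events push the percentages up. The documents do not fix the size of either effect, so the net direction is not known.

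**What to change.** In CLP-008 Sections 7.1 and 7.3 and Tables 14.8.3.1 to 14.8.3.8:

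1. Keep n (%) and add patient-years on active stimulation and events per 100 patient-years.
2. Count onset from initiation of active stimulation (Day 0 for treatment, the Week 12 crossover for control).
3. Include every subject who received any active stimulation, including those who later stopped.
4. Split the rates by time interval where data exist, because one overall rate assumes a constant hazard. An early cut will leave the late intervals empty.
5. Show events before active stimulation (surgical and sham periods) separately, and state the counting window for each column.

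The AE onset, Day 0, Week 12 and exit dates are already listed, so the cost is SAP wording, some programming and slightly longer tables. Nothing now planned is removed.

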7.2 Protocol Deviations

All protocol deviations will be tabulated with reasons for deviations reviewed by sponsor and reported in compliance with the study protocol, IRB requirements and sponsor's SOPs.

Summary tables with the number and percentage of subjects with protocol deviations will be provided by type of deviation (**Appendix B**). A by-subject listing of all protocol deviations will be provided (**Appendix C**).

7.3 Device Deficiencies

All device deficiencies related to the identity, quality, durability, reliability, safety or performance of the study device, including device malfunctions, use errors, and inadequate labelling will be tabulated. Summary tables with the number and percentage of device deficiencies will be provided by type (**Appendix B**). A by-subject listing of all device malfunctions will be provided (**Appendix C**).

8 STATISTICAL CONSIDERATIONS RELATED TO COVID-19

The statistical considerations detailed in this section are consistent with the FDA's guidance on the conduct of clinical trials during the COVID-19 pandemic and recommendations for the statistical analysis of the primary and key secondary endpoints to help ensure that the COVID-19-related changes to the RESET-RA study conduct will provide interpretable findings with correct statistical quantification of uncertainty.

8.1 Impact of COVID-19 on Study Integrity

Unavoidable protocol modifications may be required due to COVID-19 illness and/or COVID-19 control measures to protect subject safety and the to address its impact on the ability to collect data. The context and/or reasons for post-baseline events as they relate to COVID-19, such as discontinuation of treatment, withdrawal from the trial, use of alternative or rescue treatments, missed endpoint assessments, and the use of alternative endpoint assessment methods will be captured at the subject level. Information not specific to individual subjects, such as information on site closure (rheumatology or surgery) and its impact on disrupting administration of the investigational study device (i.e., implant procedure, device titration, device adjustments) will also be captured. This information at both the subject and site levels may be useful for incorporating into additional sensitivity analyses related to the impact of COVID-19.

